- d. Use of medications known to modify glucose metabolism or to decrease the ability to recover from hypoglycemia such as oral, parenteral, and inhaled steroids (as discussed above), and immunosuppressive or immunomodulating agents.
- 13. Known allergy to soy.
- 14. Subject is on a weight loss program and is not in the maintenance phase, or subject has started weight loss medication (e.g., orlistat or liraglutide), within 8 weeks prior to Screening.
- 15. Subject has had bariatric surgery.
- 16. Subject is pregnant or breast-feeding.
- 17. Subject is a user of recreational or illicit drugs or has had a recent history (within 1 year of Screening) of drug or alcohol abuse or dependence. (Note: Alcohol abuse includes heavy alcohol intake as defined by >3 drinks per day or >14 drinks per week, or binge drinking) at Screening. Occasional intermittent use of cannabinoid products will be allowed provided that no cannabinoid products have been used during the 1 week prior to each visit.
- 18. One or more contraindications to metformin as per local label.
- 19. History of gastrointestinal disorders (e.g. hypochlorhydria) with the potential to interfere with drug absorption.
- 20. At the Principal Investigator's discretion, any condition or other factor that is deemed unsuitable for subject enrollment into the study.

Statistical Methods

The primary endpoint for this study is the change from baseline in HbA1C at Visit 9 (Part 2 Week 10). Mean change from baseline to Week 12 HbA1C (Visit 9 value – Visit 3 value) will be tested using an analysis of covariance (ANCOVA) model using baseline HbA1c and whether the subject is using additional antidiabetes drugs (beyond Metformin) as covariates.

Observed means and mean changes from baseline for HbA1C and FPG will be analyzed by visit using a method similar to the primary endpoint.

Change from baseline to Week 12 (Visit 9, Part 2 Week 10) in PPG parameters during a MMTT, including AUC₀₋₆₀, AUC₀₋₁₂₀, and 1 & 2-hour PPG absolute levels and excursions will be analyzed using a method similar to the primary endpoint.

Changes from baseline to Week 12 (Visit 9, Part 2 Week 10) in mean 24-hour, mean day time (6 AM to 10 PM) and mean night time (10 PM to 6 AM) glucose as measured by CGM will be analyzed using a method similar to the primary endpoint. For a day to be included in the calculations of the overall means, the subject must have at least 80% of the expected glucose readings.

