3.2 Screening (1 to 3 Weeks prior to Visit 1)

At the Screening Visit, potential subjects will be given a detailed oral presentation describing the nature, purpose, risks, and requirements of the study and will receive detailed written information. Subjects will be given ample time to consider participation and ask questions which will be adequately addressed by site personnel.

Once the subject is satisfied that he/she is willing to participate in the study, he/she will be asked to sign the study informed consent form (ICF) (refer to Section 11.1.4 for further detail regarding the ICF). The investigational site personnel obtaining written consent from the subject will also sign the form to confirm consent has been obtained.

Once signed, the Investigator will retain the original ICF for the subject's study records and provide the subject with a signed copy. The investigator will verify that informed consent has been obtained from each subject prior to enrollment into the study and prior to the subject undergoing any study-related procedures.

Screening activities after obtaining informed consent will be conducted and consist of the following:

- Completion of medical and social history, including tobacco, alcohol, caffeine, drug use, and disease history questionnaire;
- Collection of demographic data (sex, age, race/ethnicity);
- Review of prior and current medications and supplements;
- Review inclusion and exclusion criteria.
- Physical examination.
- 12-lead electrocardiogram (ECG).
- Measurement of height and weight.
- Measurement of vital signs (SBP/DBP and heart rate).
- Collection of fasted blood and urine samples for:
 - Clinical safety labs, including hematology, serum chemistry (with FPG, A1C, C-peptide, immunogenicity testing, and serum thyrotropin/TSH), and urinalysis (see Section 6.1.5 for list of tests).
 - o Urine drug screen.
 - o Serum pregnancy test (women of childbearing potential/WCBP only).
- Remind subjects to arrive fasting for Visit 1.

For subjects who meet eligibility criteria based on the Screening assessments, instruction will be provided on the following:

- the use of adequate contraceptive methods (see Section 4.1) for the duration of the study (Screening through Follow-Up Visit 10);
- minimal use of concomitant medications during the study, if possible, and avoid prohibited medications as defined in Section 5.7:

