3.3 Run-In

3.3.1 Visit 1 (Run-In Week 0)

Subjects will report to the clinic in the morning following a 10-hour fast prior to taking morning medications. The following procedures will be performed:

- Review of prior and current medications and supplements;
- Review inclusion and exclusion criteria;
- Measurement of weight;
- Measurement of vital signs (SBP/DBP and heart rate);
- Collection of fasted blood and urine samples for:
 - Clinical safety labs, including hematology, serum chemistry (with FPG and A1C), and urinalysis (see Section 6.1.5 for list of tests);
 - o Urine pregnancy test (WCBP only);
- Perform DTSQs questionnaire.
- Provide subjects with SMBG, nutrition, and hypoglycemic symptom training.
- Provide subjects with e-diaries and instruct on how to use them to collect essential data.
- Subjects will be instructed on the proper placement and use of the CGM device and the
 device will be calibrated. NO ACETAMINOPHEN usage should occur during the CGM
 monitoring periods. Subjects should notify the study staff if they used acetaminophen (or

any acetaminophen containing products) during the CGM monitoring period. Subjects will also be provided a paper diary during the CGM period to ensure dose times and meal times are recorded.

- Provide subjects with SMBG meters and supplies (lancets and test strips) and instruct on how to use them. This will include instructions for collecting 7-Point SMBG one to two per week (within 5 days prior to their upcoming Visit), recording insulin doses, and bringing meter to every clinic visit.
- Dispense placebo with instructions for administration (Cohort A: one capsule from each bottle to be taken at bedtime @ 10 PM ± 90 minutes, each night no sooner than 2 hours after dinner; Cohort B: one capsule to be taken at bedtime @ 10 PM ± 90 minutes, each night no sooner than 2 hours after dinner).
- Record adverse events.
- Remind subjects to collect 7-Point SMBG profiles
- Remind subjects to arrive fasting for Visit 2.

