3.3.2 Visit 2 (Run-In Week 1 ± 3 days)

Subjects will report to the clinic in the morning following a 10-hour fast prior to taking morning medications. The following procedures will be performed:

- Review of prior and current medications and supplements;
- Measurement of vital signs (SBP/DPB and heart rate);
- Collection of fasted blood sample for FPG.
- Urine pregnancy test (WCBP only);
- Remove CGM device and download the data.
- Insert new CGM sensor. Subjects will be instructed on the proper placement and use of the CGM device and the device will be calibrated. NO ACETAMINOPHEN usage should occur during the CGM monitoring periods. Subjects should notify the study staff if they used acetaminophen (or any acetaminophen containing products) during the CGM monitoring period. Subjects will also be provided a paper diary during the CGM period to ensure dose times and meal times are recorded.
- Review e-diary, paper diary, and SMBG data.
- Collect unused placebo and review e-diary for compliance.
- Review e-diary for hypoglycemic events and completeness of entries.
- Re-dispense placebo with a reminder on instructions for administration.
- Record adverse events.
- Remind subjects to collect 7-Point SMBG profiles
- Remind subjects to arrive fasting for Visit 3.

3.4 Part 1

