3.9 Schedule of Events

Table 1 below describes the daily schedule of events from Screening through Follow-Up Visit 10.

Table 1. Daily Schedule of Events from Screening through Follow-Up Visit

		Rur	ı-In	Par	t 1	Part 2			Rescue	Follow- Up		
Visit	Screen	1	2	3	4	5	6	7	8	9	RV	10
Week	-3 to -1	0	1	0	1	0	1	4	8	10	Variable	12
Informed Consent	X											
Inclusion/Exclusion	X	X		X								
Medical History/Disease History Questionnaire	X											
Concomitant Medications	X	X	X	X	X	X	X	X	X	X	X	X
Physical Examination	X			X						X	X	X
12-lead ECG	X									X	X	
Height and Weight ¹	X	X		X		X			X	X	X	X
Vital Signs ²	X	X	X	X	X	X	X	X	X	X	X	X
Chemistry, Hematology, Urinalysis	X	X		X		X			X	X	X	X
Urine Drug Screen	X			X		X						
Pregnancy Test ³	X	X	X	X	X	X	X	X	X	X	X	X
C-peptide and TSH	X											
Fasting Blood Glucose	X	X	X	X	X	X	X	X	X	X	X	X
HbA1C	X	X		X		X			X	X	X	X
Immunogenicity Testing	X									X	X	X
Randomization ⁴				X								
CGM On/Off (Dispense/Review paper diary)		On		Off					On	Off		

		Rui	n-In	Par	t 1			Part	2		Rescue	Follow- Up
Visit	Screen	1	2	3	4	5	6	7	8	9	RV	10
Week	-3 to -1	0	1	0	1	0	1	4	8	10	Variable	12
Mixed Meal Tolerance Test ⁵				X						X	X	
Dispense e-diary and Train on Use		X										
SMBG/Nutrition/Hypoglycem ia Symptom Training		X		X		X						
Review e-diary SMBG data			X	X	X	X	X	X	X	X	X	
Review e-diary and assess for hypoglycemic events			X	X	X	X	X	X	X	X	X	
Collect study medication and review e-diary for compliance			X	X	X	X	X	X	X	X	X	
Dispense SB placebo		X	X									
Dispense study medication (active or placebo)				X	X	X		X	X			
Subject Training/Insulin Dosing Review ⁶				X	X	X	X	X	X	X	X	
Assess for Rescue or Termination ⁷						X	X	X	X		X	
Collect e-diary										X		
DTSQs		X				X			X		X	
DTSQc									X		X	
Adverse Events		X	X	X	X	X	X	X	X	X	X	X

Table 1 Footnotes

- ¹Height will be measured at Screening only. Weight will be measured as indicated.
- ²Heart rate and blood pressure.
- ³Serum pregnancy test at Screening, urine pregnancy test at Visits 1-10 and at Rescue Visits.
- ⁴ Randomization will occur at Visit 3. Subjects will be dispensed single-blind placebo to be taken QHS during the runin period. At Visit 3, subjects will be dispensed ORMD-0801 or placebo to be administered according to their randomization schedule. For Cohort A, subjects randomized to ORMD-0801 will start their dose at 16 mg at Visit 3, increase to 24 mg at Visit 4, and increase to 32 mg at Visit 5.

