8.3.1 HbA1C Evaluation

Mean change from baseline to Week 12 HbA1C (Visit 9 value – Visit 3 value) will be tested using an analysis of covariance (ANCOVA) model using baseline HbA1C and whether the subject is using additional antidiabetes drugs (beyond metformin) as covariates.

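### The stated efficacy ANCOVA uses one baseline reading although three HbA1C and four FPG readings precede randomised dosing; adding the earlier ones as covariates is a free, probably modest, gain in precision

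*Combined protocol and SAP*

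**What the plan says.** **Measurements.** Screening bloods include "serum chemistry (with FPG, A1C, C-peptide, immunogenicity testing, and serum thyrotropin/TSH". Visit 1 takes "Clinical safety labs, including hematology, serum chemistry (with FPG and A1C), and urinalysis", and the Visit 3 list (Section 3.4.1) has the same item. Visit 2 adds "Collection of fasted blood sample for FPG". Table 1 in Section 3.9 agrees with the visit texts, and its footnote 4 states "Randomization will occur at Visit 3". So there are three HbA1C and four FPG readings before the first randomised dose.

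**Analysis.** Section 8.3.1 states "Mean change from baseline to Week 12 HbA1C (Visit 9 value – Visit 3 value) will be tested" by ANCOVA. In the Synopsis the change is to be "tested using an analysis of covariance (ANCOVA) model using baseline HbA1c and whether the subject is using additional antidiabetes drugs" beyond metformin; Section 8.3.1 names the same two covariates, and neither place names any other. Section 8.4 states "Observed means and mean changes from baseline for HbA1C and FPG will be analyzed by visit using a method similar to the primary endpoint" and names no FPG baseline visit.

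**Other uses of early readings.** Section 8.6.3 takes Screening as baseline for laboratory changes in the safety summaries, and Section 6.1.5.1 lists glucose among those tests. Section 8.3 mentions stratification by Screening HbA1C, while Section 5.2 names other factors; under neither does Screening HbA1C enter the model. Section 8.3.2 leaves the variables in the imputation model open, and Section 8 defers further detail to the statistical analysis plan.

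**The concern.** A single reading carries assay and day-to-day variation as well as the subject's true level. Earlier readings of the same quantity help to separate the two and so should help to predict the Week 12 value. They are taken before randomised treatment starts, so treatment cannot affect them, and adjusting for them does not bias the randomised contrast. Leaving them out makes the residual variance somewhat larger than it need be.

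This matters a little more here because the design has little spare power. The calculation in Section 8.2.1 lands almost exactly on 80% for BID and TID combined against placebo. The first test in the sequence of Section 8.1 is TID alone against placebo, which has fewer subjects, and the BID and QHS tests are reached only if it succeeds.

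**Working it through.** **Inputs from the protocol.** Difference 0.6, SD 1.2, 48 completers per group, BID and TID combined v combined placebo, 80% power (Section 8.2.1); alpha 0.05 (Section 8.1). Sidedness is not given for the sample size; two-sided reproduces the figure.

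**1. The plan's own figure.**
- Controls needed at 2:1: (1 + 1/2) × (1.960 + 0.842)² × 1.2² / 0.6² = 47.1, so 48.
- Power at 96 v 48: SE = 1.2 × √(1/96 + 1/48) = 0.212; 0.6/0.212 − 1.960 = 0.868; power 80.7%.
- TID alone, 48 v 48: SE = 0.245; 2.449 − 1.960 = 0.489; power 68.8%.

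The stated size is reproduced with no allowance for covariate adjustment.

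**2. HbA1C (assumed variability).** The documents give no within-subject SD or correlation. Write X = T + e for a baseline reading and Y = bT + d + e for Visit 9, with the SD of change fixed at 1.2. Then

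residual variance with k readings = b²·varT·(se²/k)/(varT + se²/k) + var_d + se²,

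where var_d = 1.44 − (1 − b)²·varT − 2se². Assumed ranges: se 0.15–0.45, varT 1.0–1.44, b 0.8–1.0.

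| Case | k = 1 | k = 2 (Visits 1, 3) | k = 3 (with Screening) |
|---|---|---|---|
| se 0.45, varT 1.44, b 1.0 | 1.415 | 1.332 (−5.9%) | 1.302 (−8.0%) |
| se 0.15, varT 1.0, b 0.8 | 1.392 | 1.385 (−0.5%) | 1.382 (−0.7%) |

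Cross-check by correlations, for the mean of k exchangeable readings: variance ratio = [1 − kρ²/(1 + (k − 1)r_b)] / (1 − ρ²), with ρ the baseline-to-Visit-9 correlation and r_b the correlation between baseline readings. At k = 3 and assumed ρ = 0.7, r_b of 0.90, 0.95 and 0.98 gives reductions of 7%, 3% and 1%.

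**3. What that does to power**, taking 1.2 as the single-baseline residual SD:

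| Variance reduction | 96 v 48 | TID, 48 v 48 |
|---|---|---|
| 0% | 80.7% | 68.8% |
| 1% | 81.1% | 69.2% |
| 5% | 82.7% | 71.0% |
| 8% | 83.9% | 72.4% |

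A 5% reduction is worth 1/0.95 = 1.053, about 5% more subjects.

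**4. FPG (assumed variability).** With single-reading reliability I and true-level correlation r over 12 weeks, R²(k) = (rI)²·k/(1 + (k − 1)I). The reduction is 1 − [1 − R²(k)]/[1 − R²(1)]. For I = 0.5–0.8:

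| | k = 3 (Visits 1, 2, 3) | k = 4 (with Screening) |
|---|---|---|
| r = 0.6–0.8 | 4.6–11.4% | 5.3–13.3% |
| r = 1 (upper bound) | 16.7–27.4% | 20.0–31.4% |

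These calculations treat the readings as exchangeable. Equal weights are then best, so separate covariates give the same gain apart from degrees of freedom. If the readings are not exchangeable, separate coefficients can only do better in large samples, though the gain itself may differ from the table.

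**The case against.** The strongest reply is that nothing here is wrong. ANCOVA on the last pre-dose value is a standard, valid analysis, it contradicts nothing in the documents, and the sample size reproduces without any covariate adjustment. All of that stands. It does not remove the case for a change that keeps the endpoint, needs no new data and cannot bias the comparison.

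The reply on size also largely stands. Section 1 describes HbA1C as reflecting average glycaemia over several months. Screening precedes Visit 3 by roughly three to five weeks, so the three readings should agree closely and the primary-endpoint gain is probably at the low end. FPG may gain more, but it is a secondary endpoint with no stated power.

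The readings are not strictly interchangeable either. Screening predates the placebo run-in, and entry depends on an HbA1C cut at 7.5%, so regression to the mean applies to a Screening value used for selection. That does not bias the randomised contrast, since selection comes before allocation. It is a reason not to average Screening into the baseline.

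Three stronger readings are tempting and are not supported:
- A reader might infer that no analysis uses the early readings. Section 8.6.3 uses Screening as a safety laboratory baseline, and the imputation model is open. Only the stated efficacy covariates omit them.
- A reader might infer that FPG is analysed from Visit 3 as a stated rule. The visit is inferred from the reference to a similar method.
- A reader might infer variance savings of 20–31% for FPG. Those need a perfectly stable true level over 12 weeks of treatment.

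**Conclusion.** The point holds as an optional improvement. The stated efficacy ANCOVA leaves out two earlier HbA1C readings and, on the natural reading of Section 8.4, three earlier FPG readings. The analysis as planned remains valid.

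The likely size is 1–8% lower residual variance for HbA1C, more likely toward 1%, and about 5–13% for FPG with all four readings. These ranges rest on assumed reliabilities, within-subject SDs and correlations, and the power figures also treat 1.2 as the residual SD. If 1.2 is the raw change-score SD, single-baseline ANCOVA already has somewhat more power than 80.7%. The gain would not repair the lower power of the TID-alone test: even the top of the HbA1C range brings it only to 72.4%.

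**What to change.** In Section 8.3.1, keep Visit 3 as the change-score baseline and prespecify the earlier readings as additional covariates, separate from the Visit 3 value: Visit 1 HbA1C, with or without Screening HbA1C. In Section 8.4, name Visit 3 as the FPG baseline and add Visit 1 and Visit 2 FPG, with or without Screening FPG. Separate terms let the fitted coefficients down-weight Screening. The choice on Screening should be fixed before unblinding.

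In Section 8.3.2, list the same variables in the multiple-imputation model, which also deals with any missing earlier reading.

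The cost is one sentence in the analysis plan and one or two extra degrees of freedom for HbA1C, two or three for FPG. No visit, sample or endpoint changes.

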Table	1. Daily Schedule of Events	from Screening through Fo	ollow-Up Visit31
Table	2. General Guidelines for Se	verity Assessment of Adve	erse Events52

LIST OF ABBREVIATIONS AND DEFINITIONS OF TERMS

A1C HbA1C (hemoglobin A1C)

AE adverse event

ALT alanine aminotransferase AST aspartate aminotransferase

AUC area under the curve BUN blood urea nitrogen

CAN cardiac autonomic neuropathy
CFR Code of Federal Regulations
CGM continuous glucose monitoring

CHF congestive heart failure

CRO contract research organization

CTCAE Common Terminology Criteria for Adverse Events

DBP diastolic blood pressure

DTSQs Diabetes Treatment Satisfaction Questionnaire

DTSQc Diabetes Treatment Satisfaction Questionnaire Change

ECG electrocardiogram

eCRF electronic case report form

eGFR estimated glomerular filtration rate

EDC electronic data capture

EDTA ethylenediaminetetraacetic acid

EW early withdrawal FBG fasting blood glucose

FDA Food and Drug Administration

FPG fasting plasma glucose
GCP Good Clinical Practice
GGT gamma-glutamyltransferase
GLP-1 glucagon-like peptide 1
HbA1C hemoglobin A1C

HIPAA Health Insurance Portability and Accountability Act of 1996

HIV Human Immunodeficiency Virus

IB Investigator's Brochure ICF informed consent form

ICH International Council for Harmonization IND Investigational New Drug application

IRB Institutional Review Board

IUD intrauterine device

MedDRA Medical Dictionary for Regulatory Activities

MMTT Mixed Meal Tolerance test NYHA New York Heart Association

OAD oral antidiabetic
PPG post-prandial glucose
SAE serious adverse event
SBP systolic blood pressure
SBTI soybean trypsin inhibitor

SMBG	self-monitored blood glucose
SOP	standard operating procedure
T2DM	type 2 diabetes mellitus
TIA	transient ischemic attack

TEAE treatment-emergent adverse event

TSH serum thyrotropin TZD thiazolidinedione

WCBP woman of childbearing potential WHO World Health Organization

1 INTRODUCTION

Diabetes mellitus is a chronic metabolic disorder that has reached epidemic proportions in the United States, affecting almost 8% of the U.S. population in 2007, and worldwide (Centers for Disease Control and Prevention, 2008). Diabetes mellitus is defined by hyperglycemia (increased concentration of glucose in the blood) caused by defective insulin secretion (type 1), resistance to insulin action (type 2), or a combination of both. Diabetes mellitus leads to an increased risk of microvascular damage (retinopathy, nephropathy and neuropathy), reduced life expectancy, increased risk of macrovascular complications (ischemic heart disease, stroke, and peripheral vascular disease), and diminished quality of life. This illness requires continuing medical care and subject self-management and education to prevent acute complications and to reduce the risk of long-term complications (American Diabetes Association, 2009).

The World Health Organization (WHO) has established diagnosis criteria for type 2 diabetes mellitus (T2DM) of fasting plasma glucose greater than or equal to 126 mg/dL (7.0 mmol/L), plasma glucose greater than or equal to 200 mg/dL (11.1 mmol/L) at 2 hours following ingestion of 75 g anhydrous glucose in an oral glucose tolerance test, or random plasma glucose greater than 200 mg/dL (11.1 mmol/L) in a person with symptoms of diabetes (World Health Organization, 2006). The treatment goal for subjects with this disease is long-term glycemic control (over both fasting and non-fasting blood glucose levels), which has been demonstrated in both type 1 and type 2 subjects to reduce the morbidities associated with uncontrolled glycemic levels (Diabetes Control and Complications Trial Research Group, 1993; Cleary et al., 2006; UK Prospective Diabetes Study Group, 1998a & 1998b). Typical options for glycemic control in subjects with T2DM include lifestyle management (diet and exercise), exogenously administered insulin, insulin plus oral drugs such as metformin or sulfonylureas, and oral drugs alone. Glycemic control is measured by subject self-monitored blood glucose (SMBG), subject selfmonitoring of interstitial glucose, and periodic blood tests for measurement of hemoglobin A1C (HbA1C; A1C). HbA1C levels reflect average glycemia over several months and therefore provide a surrogate for glycemic control (U.S. Food and Drug Administration, 2008). A consensus statement written by the American Diabetes Association and the European Association for the Study of Diabetes targets an HbA1C level of <7% as an objective for nonpregnant adults, who do not have complicating factors, for the prevention of micro- and macrovascular disease (Nathan et al., 2009).

In addition to lifestyle modification through diet and exercise, a number of treatments are available to treat hyperglycemia in diabetic subjects. The choice of antihyperglycemic agents is made between physicians and subjects based upon the agents' effectiveness in lowering glucose, other effects that can reduce long-term complications, safety, tolerability, ease of use, and expense. For example, metformin is widely prescribed as an initial therapy to improve glycemic control in subjects with T2DM. It decreases hepatic glucose output and lowers fasting glycemia, thereby reducing HbA1C levels. It is generally well-tolerated, with possible gastrointestinal adverse events and low incidence of hypoglycemia, but is contraindicated in subjects with renal dysfunction. Sulfonylureas lower glycemia by enhancing insulin secretion, and are effective in lowering HbA1C levels. Possible adverse events associated with this class of drugs include hypoglycemia (more frequent in elderly subjects) and weight gain. Other drugs such as thiazolidinediones (TZDs), glucagon-like peptide 1 (GLP-1) analogue, α-glucosidase inhibitors, glinides, and pramlintide are commercially available in the U.S., but are considered less well-

validated with respect to established use, efficacy, and cost-effectiveness for achieving target glycemic goals than lifestyle management, metformin, and sulfonylureas (Nathan et al., 2009).

Subcutaneously administered insulin is highly effective at lowering glycemia and helping subjects achieve target HbA1c levels. Insulin has no overall dose limit with respect to safety and provides an improved lipid profile. However, subcutaneously administered insulin requires daily injections and blood glucose monitoring, and is associated with weight gain and an increased risk of hypoglycemia. Insulin is available as formulations with different pharmacokinetic (PK) and pharmacodynamic (PD) profiles (e.g, rapid, regular, intermediate, or long acting, or mixtures of these). These different formulations are used (Nathan et al., 2006) to tailor appropriate insulin regimens on a per subject basis.

Oramed Ltd. is developing a proprietary oral formulation of recombinant human insulin (ORMD-0801). Oramed, located in Jerusalem, Israel, was established in 2006 and the company's proprietary platform technology is based on over 25 years of medical research at the Hadassah University Medical Center in Jerusalem, Israel.

ORMD-0801 is based on Oramed's- platform technology for the oral delivery of polypeptides, which includes a proprietary formulation of excipients to facilitate oral uptake by hindering proteolysis in the small intestine and facilitating translocation of peptides across the gut epithelial lining, and into the systemic circulation. The formulation for ORMD-0801 includes soybean trypsin inhibitor (SBTI) to hinder proteolysis, and disodium ethylenediaminetetraacetic acid (EDTA) to facilitate translocation. Fish oil provides omega-3 fatty acids. The enteric-coated capsules are designed to disintegrate in a pH-dependent manner in the small intestine. The initial indication for ORMD-0801 is improvement of glycemic control in adult patients with diabetes mellitus.

The potential advantage of oral insulin in the treatment of elevated fasting blood glucose as compared to subcutaneously-administered insulin lies in its delivery to the hepatic portal vein. Orally-administered insulin, once transported across the gut wall, is ferried to the hepatic portal vein, mimicking the natural route of endogenous pancreatic insulin and delivering the insulin directly to the intended site of action. In contrast, subcutaneously-administered insulin reaches the liver through the systemic circulation thereby requiring higher systemic levels of insulin in order to achieve the same effect. Thus, oral insulin administration is expected to avoid systemic hyperinsulinemia and provide a reduced risk of hypoglycemia. The PK/PD profile of ORMD-0801 is well-suited to the control of both fasting blood glucose and subsequent pre-meal blood glucose levels due to the delayed onset of glucose lowering activity. Therefore, Oramed is pursuing oral administration of ORMD-0801 at bedtime and one or two other times during the day for the improvement of glycemic control in adult subjects with type 2 diabetes mellitus.

Oramed has completed five Phase 1 safety studies of various formulations of ORMD-0801 in healthy human volunteers. Four Phase 2 studies have been completed, two in subjects with type 2 diabetes, and two in subjects with type 1 diabetes. These Phase 2 studies investigated different formulations, the effect of meals at different times following ORMD-0801 administration, and the effect of ORMD-0801 on glucose as measured by continuous glucose monitoring over a ten day treatment period with three doses per day prior to meals. One Phase 2 study assessed the safety and effectiveness on fasting blood glucose of repeat bed time administration of ORMD-

0801 in subjects with type 2 diabetes over a period of six weeks. In ORA-D-007, the difference in mean HbA1C in the ORMD-0801 combined group vs. the placebo group was statistically significant and at all doses tested, ORMD-0801 was as well tolerated as placebo and was not associated with any serious AEs related to the drug. More recently, ORA-D-012 (Phase 2a) evaluated the effect of ORMD-0801 on glucose (continuous glucose monitoring) administered qd, bid, or tid and concluded that there was a benefit to dosing multiple times per day. These studies demonstrated that the drug product is well-tolerated and can effectively reduce plasma glucose levels. There were no significant safety observations and no serious adverse reactions were reported for the completed studies, although there were two self-reported events of hypoglycemia in the 6-week, Phase 2 study.

